8 STUDY COMPLETION AND REMUNERATION

Once their involvement in the study is complete, participants will be informed about receiving feedback following study completion in the Letter of Appreciation (Appendix 11).

Participant remuneration will be \$180 for completing the study and is typically paid at the end of the study (Appendix 12). This remuneration can be in a form of cheque or Amazon gift card and participants will be asked to choose one of the two options. One pair of the study lenses may be kept by participants at the end of the study as long as they continue care with UW-CLC or their own contact lens specialist.

9 STATISTICAL ANALYSIS AND DATA MANAGEMENT

9.1 STATISTICAL ANALYSIS

All data described above will be analysed at the University of Waterloo from the eyes wearing the scleral lenses. Data analysis will be conducted using Statistica 13. Descriptive statistics will be used to analyse the baseline variables (age, gender, sagittal depth distribution, etc.). Table 3 lists the primary outcome variables and anticipated statistical procedures.

Table 3: Statistical procedures

| Variable | Analysis | Statistical test |
|---|---|------------------------------------|
| Parametric: tear clearance, corneal thickness, epithelial thickness, curvature, vision, osmolarity, comfort ratings | Comparison of lenses 1, 2 Comparison of epithelial and corneal thickness evaluation, osmolarity measurements | Paired t-test ANOVA RM-ANOVA |
| Nonparametric: OSDI, SPEED, CLDEQ-8, levels of protease | Comparison of ocular symptoms, quality of life, dryness, subjective assessment | T-test Mann-Whitney U test |

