4 MATERIALS AND METHODS

4.1 STUDY DESIGN

4.1.1 OVERALL DESIGN

This will be a prospective, dispensing cross over study design involving five visits.

The first visit will involve screening, baseline measurements and trial fitting of scleral lenses. At this visit, participants may be wearing their habitual contact lenses (if any) as prescribed by their Optometrist/Ophthalmologist.

The second visit will be a dispensing visit of one of the pairs of the scleral contact lens designs (with or without Hydra-PEG, randomly assigned) and a single follow up visit after 8-10 hours of lens wear in a day, four weeks later (third visit). A washout period of a minimum of 48 hours will be applied between lens types. The fourth and fifth visits will be for the other scleral contact lens visits (delivery and after 4 weeks).

Scleral contact lenses to be worn in this study will be made of Boston XO material (with and without Hydra PEG) approved by Health Canada for commercial purposes. The scleral contact lenses will have a diameter of 14.8-15.4mm. The manufacturer's recommended guidelines will be used to select and fit these lenses, with an expected corneal clearance between 250 μ m to 350 μ m. As to which of the two scleral contact lenses are being assessed, both the investigator and the participant will be masked as the Optometric assistant will provide the lenses in an unlabelled case.

Masking the investigator will prevent bias when measuring the primary outcome variables and analyzing the data.

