4.2 STUDY POPULATION

4.2.1 SAMPLE SIZE CALCULATION

A minimum sample of 20 DE participants are required to complete the study and thus 25 DE participants will be enrolled. The standard deviation used to determine the sample size was derived from a previous study involving a comparison of fitting scleral contact lenses of different vaults in keratoconus patients and from evaluation of cornea thickness in controls and those having keratoconus (a plausible comparative group).

Power (i.e. the probability of correctly rejecting the null hypothesis) required for this study/experiment is 90% and type-I error is set to 0.05.

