4.3.9 SCLERAL CONTACT LENSES

Zen™ RC scleral lenses (non-coated, and Hydra-PEG coated) to be used in this study are approved by Health Canada and are commercially available (license #96602). They are manufactured using the Boston XO material (Health Canada license #71386). All lenses will be worn during the day only. Lenses will be fitted according to manufacturer's recommended guidelines and participants will proceed in the study only if a suitable fit with the lenses can be obtained. This type of conventional lens design will be fitted on both eyes. Appendices 14 and 15 (Package insert for Boston XO and Zen™ RC Fitting Guide respectively).

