4.5 STUDY PROCEDURES

4.5.1 SCREENING AND BASELINE MEASUREMENTS

Screening & Baseline procedures: Participants will present to the screening visit. The cornea sagittal depth/height will be measured with the Visante OCT. OSDI and SPEED will be collected from the participant. Confirmation and change of dry eye status will be assessed based on tear

osmolarity and MMP-9 measurements using the Tearlab Osmolarity System and InflammaDry® test kits respectively. Additionally, their auto-refraction, visual acuity measurements as well as corneal topography with the Pentacam will be carried out. Eligibility will be confirmed, and a baseline biomicroscopy assessment will be performed to assess corneal. (Visit 0-0).

Ocular Surface Imaging: The eyes of the participants will be examined at the slit-lamp biomicroscope and imaged using the Keratograph® 5M. Participants will be seated at the Keratograph® 5M instrument and asked to blink 2-3 times and hold their eyes open for a few seconds until the instrument software takes a picture of the eye. This image acquisition will be repeated twice. This procedure will also be used to assess corneal and conjunctival staining. (Visits 0-0; 1-1; 2-2).

Fitting of the scleral lenses: Participants will be trial fitted with a scleral lens design using the Pentacam software and following the manufacturer's recommendation, but one pair will be ordered non-coated and the other pair will be Hydra-PEG coated (randomly selected). Acceptable fitting will be based on manufacturer's recommended guidelines for fitting these lenses. All scleral lenses used in the study will be made of Boston XO material. Participants will be instructed on insertion, removal, and proper handling of lenses (Visits 0-0, 1-1 2-1).

Imaging procedure With and Without Test Lenses: The anterior segment of the eye and the lens fit will be imaged and assessed using the Visante OCT, Keratograph 5M, Pentacam and Spectralis OCT prior to lens wear and after the lens delivery appointment (Visits 1-1, 2-1), and at the follow up appointment (Visits 1-2, 2-2).

Corneal Thickness Measurements: Corneal thickness will be measured with the Spectralis OCT and Pentacam before and after lens wear (Visits 0-0, 1-2, 2-2). Participants will be seated at the Spectralis OCT and the Pentacam instruments and to blink 2-3 times then hold their eye open for a few seconds until the instrument software takes a measurement of the corneal thickness. This measurement will be repeated twice.

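### Section 9.1 does not fix the unit of analysis although both eyes wear the same lens type in each period; entering fellow eyes as separate cases would raise the type I error of the lens comparison above 0.05 if their lens differences are positively correlated

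*Combined protocol and SAP*

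**What the plan says.** Three parts of the protocol describe treatment by pair. Section 4.3.9 states: "This type of conventional lens design will be fitted on both eyes". Section 4.1.1 assigns lenses by the pair: "The second visit will be a dispensing visit of one of the pairs of the scleral contact lens designs". Section 4.5.1 confirms that a pair is of one type: "one pair will be ordered non-coated and the other pair will be Hydra-PEG coated". Within a period, therefore, a participant's two eyes share the lens type, the period and the wearing schedule.

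On analysis, section 9.1 states: "All data described above will be analysed at the University of Waterloo from the eyes wearing the scleral lenses". For the parametric variables (corneal and epithelial thickness, osmolarity, tear clearance, curvature, vision and comfort ratings), Table 3 lists a paired t-test, ANOVA and RM-ANOVA. No section chooses one eye, averages the two, or models the participant as a cluster.

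The sample size in section 4.2.1 is in participants: "A minimum sample of 20 DE participants are required to complete the study", with 25 to be enrolled, 90% power, and "type-I error is set to 0.05". The corneal thickness procedure in section 4.5.1 uses the singular ("hold their eye open for a few seconds until the instrument software takes a measurement of the corneal thickness"), while the Keratograph procedure in the same section uses the plural. The only visible rule for recording two eyes separately is the one for adverse event forms in section 12.3.2.

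**The concern.** Both eyes wear the study lenses, so the phrase in section 9.1 selects neither of them. Taken literally, it sends data from both eyes into tests that treat each case as independent. Fellow eyes are exposed to the same lens type, period, care system and wear hours, so their coated-minus-uncoated differences may well move together. If they do, 40 eye records carry less information than 40 independent cases, the standard error is too small, and a false lens difference becomes more likely than the 5% the plan sets.

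Corneal and epithelial thickness are named primary outcomes and are measured on the eye. Osmolarity, also primary, is exposed if it is recorded per eye. The questionnaires are answered once per participant and are not affected. Because the unit is not stated, it could also be chosen after the data have been seen.

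**Working it through.** **The plan's own figure.** The 20 completers cannot be reproduced, because section 4.2.1 gives neither a numerical standard deviation nor a target difference. The step from 20 to 25 agrees with 20% loss (20 / 0.80 = 25), although no rate is stated. The check needs only the number of participants and the 0.05.

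**Inputs**
- n = 20 participants completing, and nominal error 0.05 (section 4.2.1). The number of sides is not stated; two-sided is assumed, with the one-sided result alongside.
- 2 eyes per participant, same lens type within a period (sections 4.1.1, 4.3.9 and 4.5.1).
- 2 × 20 = 40 eye records. This product is an assumption; it is not a figure in the documents. It requires that both eyes are measured and that both are entered as cases.
- r, the correlation between the right-eye and left-eye coated-minus-uncoated differences. The documents do not give it; 0 to 1 is assumed. It is not the correlation of the raw measurements, because whatever is constant within an eye cancels in the lens difference.

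**Formulae**, with the variance of one eye's lens difference set to 1
- True variance of the mean of the 40 differences: (1 + r) / 40.
- Variance the paired t-test estimates, on average: (1 − r/39) / 40. The sum of squares is (1 + r)χ²(19) + (1 − r)χ²(20), with mean 19(1 + r) + 20(1 − r) = 39 − r.
- True standard error over the estimated one: √[(1 + r) / (1 − r/39)]. At r = 0.5 this is √(1.5 / 0.987) = 1.23.
- Large-sample two-sided error: 2[1 − Φ(1.96 / √(1 + r))]. At r = 0.5 this is 2[1 − Φ(1.600)] = 11.0%.
- Finite-sample error: the t statistic from the distributions above, referred to t on 39 df, by simulation.

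**Results for 20 participants entered as 40 records**

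| r | True / estimated SE | Large-sample, two-sided | Finite-sample, two-sided | Finite-sample, one-sided 0.05 |
|---|---|---|---|---|
| 0 | 1.00 | 5.0% | 5.0% | 5.0% |
| 0.1 | 1.05 | 6.2% | 6.2% | 5.8% |
| 0.3 | 1.14 | 8.6% | 8.6% | 7.5% |
| 0.5 | 1.23 | 11.0% | 11.1% | 9.1% |
| 0.9 | 1.39 | 15.5% | 16.2% | 12.0% |
| 1 (limit) | 1.43 | 16.6% | 17.4% | 12.7% |

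The limit has a closed form. At r = 1 the statistic is √(39/19) = 1.433 times a t variable on 19 df, so the error is 2P(T₁₉ > 2.023 / 1.433) = 2P(T₁₉ > 1.412) = 17.4%. If all 25 enrolled complete (50 records), the two-sided figures are 11.1% at 0.5, 16.0% at 0.9 and 17.2% at 1.

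An RM-ANOVA on the two lens levels with the eye as case gives the same error rates, because F = t².

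**Check of the remedy.** Averaging the two eyes and testing 20 participant differences on 19 df gives a simulated error of 5.0–5.1% across the range of r. A mixed model with only participant and eye-within-participant intercepts does not help: both cancel in the lens difference, and the simulated error stays at 8.7% at r = 0.3, 11.1% at 0.5 and 16.0% at 0.9. Adding a participant-by-lens random effect brings it to 5.0–5.1%.

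**The case against.** The strongest reply is that the documents never describe the analysis that does the harm. They do not say that both eyes are measured for each outcome, or that each eye becomes a case. The sample size counts participants, no eye count appears anywhere, and the thickness procedure speaks of one eye. The plural in section 9.1 may simply be plural across participants and name the source of the data. The Study Visit Form (Appendix 6), which might show what is recorded per eye, is not in the text available.

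This stands as far as it goes: the inflation is conditional. It does not remove the gap. The wording alternates between one eye and both, nothing says which eye would be used if only one is, and a recording form would not settle the unit of analysis.

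Three stronger readings are tempting, and the documents support none of them.
- A reader might infer that the trial will run at a 17% error rate. That figure is a limit at r = 1, where both eyes show identical lens differences; any independent measurement error keeps r below 1. If the differences are mostly measurement error, the inflation is small.
- A reader might infer that a three-level RM-ANOVA (baseline and two lenses, following the visits at which thickness is measured) makes the false lens difference more likely still. Its null is that all three levels are equal, so a rejection can come from baseline versus wear; it is not evidence about the coated-versus-uncoated contrast. As the text reaches us, Table 3 also does not show which test belongs to which comparison.
- A reader might infer that osmolarity is certainly affected. Section 4.3.6 and Table 2 name the device and the form but do not say that readings are kept per eye.

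An RM-ANOVA with a correct participant-level error term would avoid the problem, but section 9.1 does not specify one.

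**Conclusion.** The concern holds in conditional form and is worth fixing before analysis. The omission is certain: lenses are assigned by pair and fitted on both eyes, and section 9.1 has no step for fellow eyes. The consequence rests on three assumptions: both eyes are measured, both are entered as separate cases, and r is positive. Under these, the two-sided error of the paired lens comparison lies above 5% and below 17.4%, for example 8.6% at r = 0.3 and 11.1% at 0.5; for a one-sided test the limit is 12.7%. The documents cannot narrow this range. No figure is offered for the plain ANOVA, protease levels, CLDEQ-8 or CLIQ. Confidence is medium, because the text permits the faulty analysis without committing to it.

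**What to change.** Add one or two sentences to section 9.1. State that the participant is the unit of analysis. State that for every variable recorded per eye (corneal and epithelial thickness, and osmolarity, tear clearance, curvature and vision where recorded per eye) the two eyes are averaged per participant, visit and lens before the lenses are compared. A mixed model is an acceptable alternative only if it includes a participant-by-lens random effect.

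The change needs no extra data or visits. If fellow-eye differences are truly independent, 95% intervals become about 3% wider: the t quantiles are in the ratio 2.093 / 2.023 = 1.035, and the ratio of mean half-widths is 1.028. At positive correlations the averaged intervals are wider than the 40-record ones by more than this, but there the wider interval corrects overstated precision and is not a real cost.

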2 PURPOSE AND HYPOTHESIS

The purpose of this study is to investigate the effects of scleral contact lens wear on a DE population using coated (Hydra-PEG) and uncoated (control) lenses. Symptoms of DE, quality of the tear film, quality of life, epithelial and overall corneal thickness, vision and comfort will be assessed before and after dispensing and wearing the lenses for four weeks.

The hypothesis is that **coated scleral contact lens wear is associated with improved ocular surface health in patients with dry eye disease (DED)**.

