At each of the follow up appointments, evaluation of lens fit, measurements of corneal thickness and assessment of the cornea with slit-lamp biomicroscope will be repeated while the participant is wearing the lenses. Immediately after the scleral lens is removed, the tears will be collected from the bowl of the lens for analysis. Other primary outcome variables (e.g., other questionnaires) will also be collected and reviewed for completeness. (Visit 1-2, 2-2).

A wash-out period of minimum of 48 hours is required between the first lens, follow up visits and the second pair of lenses (scleral lenses). Table 1 Provides a summary of the study visits.

Table 1 Summary of the study visits.

| Visit code | Visits | Time |
|--|---|---------|
| 0-0 | Screening, baseline measurements and trial lens fitting | 2.5hrs |
| 1-1 | First lens delivery visit (scleral lenses with or without Hydra-PEG) - Lens 1 | 2.0hrs |
| 1-2 | Follow-up visit (scleral lenses with or without Hydra-PEG)- Lens 1 | 1.5 hrs |
| Wash-out Period (48hours minimum) | | |
| 2-1 | Second lens delivery visit (scleral lenses with or without Hydra-PEG)- Lens 2 | 1.5hrs |
| 2-2 | Follow-up visit (scleral lenses with or without Hydra-PEG)- Lens 2) | 1.5 hrs |

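### Table 3 states no period term and no balance of lens order for a two-period crossover, and labels the contrast with numbers that Table 1 uses for delivery order: a minor gap that is cheap to close

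*Combined protocol and SAP*

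**What the plan says.** Section 4.1.1 describes a crossover with two four-week wear periods. The pair worn first is "with or without Hydra-PEG, randomly assigned". No ratio, blocking or balance of the two orders is stated there or elsewhere. Section 2 sets the question as the effect of lens wear "using coated (Hydra-PEG) and uncoated (control) lenses".

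Table 1 (section 4.4.2) numbers the lenses by delivery: "First lens delivery visit (scleral lenses with or without Hydra-PEG) - Lens 1", then "Second lens delivery visit (scleral lenses with or without Hydra-PEG)- Lens 2". In that table each number can be either coating.

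Table 3 (section 9.1) has two rows:
- The parametric row includes the contrast "Comparison of lenses 1, 2" and lists "Paired t-test ANOVA RM-ANOVA". It gives no factors or model terms.
- The other row, "Nonparametric: OSDI, SPEED, CLDEQ-8, levels of protease", lists "T-test Mann-Whitney U test" for symptoms, quality of life and subjective ratings. It does not name the lenses, but CLDEQ-8 is collected for each pair, so it presumably also compares lenses.

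Neither period nor sequence is mentioned as an analysis term. CLIQ is a primary outcome in section 3 but is not in Table 3's variable list.

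**The concern.** In a two-period crossover, each participant's coated-minus-uncoated difference contains the coating effect plus or minus any difference between the periods, with the sign set by order. A paired t-test coded by coating treats that period shift as noise. If the orders are unequal among completers, part of the shift also enters the estimate, in a direction set by chance. With about 20 completers there is little power to spare.

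The documents do not show a period effect, but they leave room for one. Section 4.2.2 does not require current lens wear, and several outcomes are self-rated. On the other side, section 4.5.1 has lens handling taught from the screening visit, which weakens a learning argument.

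Two smaller matters belong with this. The lens numbers in Table 3 should not be open to being read as delivery order. And the Mann-Whitney U test is for independent samples, whereas the two lens values come from the same person.

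**Working it through.** **Inputs.** Section 4.2.1 gives 20 completers, 25 enrolled, 90% power and type I error 0.05. It states no sidedness, effect size or SD value. Assumed here: a two-sided test; one normally distributed paired difference per participant; a period effect of 0.2 or 0.5 SD of that difference.

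**Step 1: the plan's own figure.** The 20 cannot be reproduced without an effect size, so I solved for the effect that it implies. For a paired t-test with 19 df and noncentrality δ√20, power 0.90 gives δ = 0.7645 SD. The normal approximation gives (1.960 + 1.282)/√20 = 0.725. Enrolment of 25 fits an implied 20% dropout: 20/0.8 = 25.

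**Step 2: model.** Let d = coated minus uncoated. Then d = τ + sπ + e, with e ~ N(0,1), s = +1 if coated was worn first and −1 otherwise, and π = period 1 minus period 2. Set τ = 0.7645.

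**Step 3: paired t-test by coating.** The mean of d is τ + π(n₁ − n₂)/20, where n₁ and n₂ are the completers in each order.
- At 10/10 there is no shift, but the expected variance rises to 1 + π²·20/19, which is 1.04 at π = 0.2 and 1.26 at π = 0.5.
- At 12/8 the shift is 0.2π, which is 0.04 or 0.10 SD.

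**Step 4: adjusted for period.** The estimate is the average of the two sequence means, with SE ½√(1/n₁ + 1/n₂) and 18 df. The period effect cancels, so power does not depend on π.
- At 10/10, SE = 0.2236 and noncentrality = 3.42.
- At 12/8, SE = 0.2282 and noncentrality = 3.35.

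Power, unadjusted (simulated, at least 300,000 trials per cell) and adjusted (exact noncentral t):

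| Order among 20 completers | π = 0 | π = 0.2 | π = 0.5 | Adjusted, any π |
|---|---|---|---|---|
| 10/10 | 90.1% | 89.3% | 84.8% | 89.8% |
| Blocked 13/12, 5 random dropouts | 90.0% | 89.2% | 84.3% | 89.5% |
| Simple randomisation | 90.0% | 88.8% | 82.6% | 88.1% |
| 12/8, shift against coating | – | 85.9% | 73.2% | 88.6% |
| 12/8, shift towards coating | – | 92.0% | 92.8% | 88.6% |

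**Step 5: type I error of the paired test** at π = 0 / 0.2 / 0.5:
- simple randomisation: 5.0 / 4.9 / 5.0%;
- blocked with dropout: 5.0 / 4.8 / 3.4%;
- 10/10: 5.0 / 4.6 / 2.9%.

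**Step 6: break-even.** Under simple randomisation the unadjusted test has 88.3% power at π = 0.25 and 87.5% at π = 0.3, against 88.1% adjusted. Adjustment therefore gains only above about 0.25 SD. At 0.2 SD it loses 88.8 − 88.1 = 0.7 points. With blocked order it gains 89.5 − 89.2 = 0.3 points at 0.2 SD and 89.5 − 84.3 = 5.2 points at 0.5 SD.

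**Step 7: how often splits are unequal.** Under simple randomisation, 12/8 or worse occurs 50% of the time, and exactly 12/8 has probability 12% in each direction. With 13/12 blocking and 5 random dropouts, 12/8 or worse occurs 16% of the time and exactly 10/10 36%.

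**Step 8: methods already listed.**
- RM-ANOVA with lens type within and sequence between participants (Type III sums of squares) gave the same test as the crossover model on a simulated dataset (t = 1.648, 18 df in both). At 12/8 and π = 0.5, Type III holds 5.0% type I error, while Type I sums of squares give 7.0%.
- Mann-Whitney on period differences between sequences has 86 to 87% power on normal data, with type I error of 4.2 to 4.8%.

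**The case against.** The strongest reply is that nothing is actually wrong. The purpose and objectives fix the comparison as coated versus uncoated. The investigator is masked, including for analysis (section 4.1.1), so neutral numbers in a table of anticipated procedures are natural. RM-ANOVA is already listed and can carry sequence. The paired t-test by coating is valid on average, no period effect is documented, and at 0.2 SD the loss is about one point. Under simple randomisation, adding a period term at 0.2 SD would even cost a little power.

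Most of this stands, and it keeps the point minor. What remains is that the RM-ANOVA factors are unstated, that the result at an unequal split depends on how it is set up, and that no balance of order is stated.

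A reader might go further and infer that the plan will test first pair against second pair. Such a test would miss the coating effect: with no period effect it would reject only 1.5% of the time at 10/10, or 5% under simple randomisation, despite the full 0.764 SD effect. Sections 2, 3 and 4.1.1 make that reading unlikely, so it carries no weight in the verdict. Nor is the row that names the lenses shown to be the only between-lens comparison, since the second row plausibly makes one too.

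**Conclusion.** The point holds as a minor one, and the remedy is a cheap improvement. The lens numbering is a wording ambiguity. The substantive gap is that no period term, no RM-ANOVA factors and no balance of order are stated.

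The consequence is conditional on the periods differing. With 20 completers, a back-solved effect of 0.764 SD and a two-sided 5% test, average power falls from 90% to about 89% at an assumed 0.2 SD period effect, and to 83 to 85% at 0.5 SD. An exact 12/8 split at 0.5 SD gives 73% or 93%, depending on direction. The size of the loss rests wholly on that assumed range.

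A reader might infer that the paired t-test is invalid or inflates false positives. The calculation does not support that: averaged over the allocation, type I error is at or below about 5%. Nor do the documents show that a period effect exists. Carryover across the washout, which is at least 48 hours, is a separate matter and is not addressed here.

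**What to change.** 1. In Table 3, name the contrast as coated versus uncoated.
2. Randomise order in blocks, so that the sequences are as near equal as 25 enrolled allows. Blocking cannot guarantee equality among completers.
3. For continuous outcomes, specify the listed RM-ANOVA with lens type as the within-participant factor, sequence as the between-participant factor and Type III sums of squares. A crossover model with lens, period and sequence is equivalent for completers. Both eyes are fitted (section 4.3.9), so use one value per participant and lens, for example the mean of the eyes.
4. For CLDEQ-8 and protease, do not apply the Mann-Whitney U test to the paired lens values as if they were independent. Apply it to within-participant period differences, compared between the two sequences.
5. Assign CLIQ to one of these two analyses.

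The cost is Table 3 wording, one model statement and a blocked list, with no extra participants, visits or measurements. If there is no period effect, power falls by 0.2 points (90.0 to 89.8%) at 10/10 and 0.5 points (to 89.5%) with blocking and random dropout. Without blocking it falls by about 2 points (to 88.1%), which is why items 2 and 3 should be adopted together. The rank-based test costs about 3 to 4 points if the data are normal.

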3 OBJECTIVES

The specific objectives are:

1. To evaluate the impact of coated and non-coated scleral contact lenses on DE symptoms.
2. To assess the impact of the lenses on ocular surface health.
3. To measure the comfort and quality of life ratings of each lens type.
4. To determine the subjective ratings of each pair of lenses.

The primary outcome variables are:

1. Epithelial and corneal thickness
2. Quality of the tear film (osmolarity)
3. Levels of protease (inflammatory markers)
4. Contact Lens Impact on Quality of Life (CLIQ) questionnaire score
5. Contact Lens Questionnaire-8 (CLDEQ-8) questionnaire score

Other variables of interest:

- Hours of wear
- Subjective ratings of comfort, dryness, vision and burning.

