Visual Acuity Assessment: At the screening and follow up appointments (after four weeks of each lens wear), visual acuity will be assessed using the standard LogMAR visual acuity chart. (Visits 1-2 & 2-2).

Contact Lens Dry Eyes, Quality of life assessment and Wearing experience: CLDEQ-8 (biweekly), CLIQ (weekly) and wearing habit/experience along with subjective grading scales (daily) will be used to assess ocular symptoms, quality of life and wearing experience of each of the two pairs of lenses following the four weeks wearing schedule (8-10hrs daily wear). (Visits 1-2, 2-2). These questionnaires will be filled by the participants daily, weekly, and biweekly respectively for each of the pairs of lenses for the four-weeks wearing schedule.

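### Table 3 names an independent-samples rank test (Mann-Whitney U) for two primary outcomes of a crossover, with no paired rank test and a t-test not stated to be paired

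*Combined protocol and SAP*

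**What the plan says.** Section 4.1.1 sets the design: "This will be a prospective, dispensing cross over study design involving five visits". After the first lens has been worn and a washout has passed, "The fourth and fifth visits will be for the other scleral contact lens visits (delivery and after 4 weeks"). The same people therefore supply both coated and uncoated values.

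Section 3 lists protease levels and "Contact Lens Questionnaire-8 (CLDEQ-8) questionnaire score" among the primary outcome variables.

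Table 3 in Section 9.1 has two rows:

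- The parametric row (thickness, osmolarity, vision, comfort and others) carries "Paired t-test ANOVA RM-ANOVA" and mentions a comparison of lenses 1 and 2.
- The other row is labelled "Nonparametric: OSDI, SPEED, CLDEQ-8, levels of protease" and carries "T-test Mann-Whitney U test". Its Analysis column names topics (symptoms, quality of life, dryness, subjective assessment) but no groups, pairing or sequence.

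Several values per lens are available. Section 4.3.9 says "This type of conventional lens design will be fitted on both eyes". Section 4.5.1 schedules "CLDEQ-8 (biweekly), CLIQ (weekly) and wearing habit/experience along with subjective grading scales (daily") for each pair of lenses. Section 9.1 does not say which of these values enters a test.

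**The concern.** Mann-Whitney U compares two independent samples. The protocol defines no independent groups: there is one dry-eye population wearing two lenses in turn. A comparison of baseline with follow-up would be within-person as well. Treating the two sets of values as independent puts person-to-person variation back into the error term, and removing that variation is the main reason to run a crossover. With 20 completers there is little room for this, and a null result on CLDEQ-8 or protease could be read as no effect of the coating when the test was insensitive.

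The t-test listed beside it might resolve the matter if it is paired, but the row does not say so. Two tests that can give different answers are left open for the same primary outcomes.

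**Working it through.** **The plan's own figure.** Section 4.2.1 gives 20 completers, 25 enrolled, 90% power and type I error 0.05. It gives no effect size, no SD value, no within-person correlation and no sidedness, so the 20 cannot be reproduced. The 25 agrees with 20 / (1 − 0.20) = 25 if 20% dropout is assumed.

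**Reference effect.** I took two-sided 0.05 and solved for the effect that 20 pairs detect with 90% power by paired t-test. The normal approximation gives (1.960 + 1.282) / √20 = 0.725 SD of the differences; the noncentral t gives 0.764. I used 0.764.

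**Set-up.** Bivariate normal pairs, unit SD per lens, one value per lens per participant, n = 20, within-person correlation ρ (assumed). The SD of the differences is √(2(1 − ρ)), so the lens shift is 0.764 × √(2(1 − ρ)). There were 20,000 simulated trials per cell.

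| Assumed ρ | 0 | 0.3 | 0.5 | 0.7 | 0.8 |
|---|---|---|---|---|---|
| Mann-Whitney U, power | 90% | 81% | 68% | 40% | 20% |
| Signed-rank, power | 89% | 88% | 89% | 89% | 88% |
| Mann-Whitney U, true type I error | 4.9% | 2.2% | 0.8% | 0.2% | <0.1% |
| Completers for Mann-Whitney U to reach 90% power | 20 | 26 | 32 | 45 | 62 |

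The signed-rank test rejects about 4.9% under the null throughout. A whole-number score with ties (assumed SD 6 points, 3,000 runs) gives nearly the same power: Mann-Whitney U 90 / 82 / 66 / 39 / 19%, signed-rank 88 to 90%.

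**Hand check at ρ = 0.5, using the unpaired t-test.**
- The unpaired standard error is √(2/20) = 0.316. With a critical value of 2.024 on 38 df, the threshold is 2.024 × 0.316 = 0.640.
- The true standard error is √(2 × 0.5/20) = 0.224, and the shift is 0.764 × √1 = 0.764.
- (0.764 − 0.640) / 0.224 = 0.55, which gives power of about 71%.

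Simulation also gives 71% for the unpaired t-test, against 90% paired. An unpaired reading of the listed t-test therefore does not rescue the row.

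**Protease recorded as positive/negative** (assumed 70% v 30%, latent correlation as above):

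| Assumed ρ | 0 | 0.3 | 0.5 | 0.7 | 0.8 |
|---|---|---|---|---|---|
| Exact McNemar, power | 59% | 67% | 75% | 82% | 85% |
| Mann-Whitney U, power | 71% | 71% | 74% | 75% | 76% |

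Here the paired test gains power only at high correlation. The reason to use it is validity for paired data.

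All these figures assume one value per lens per participant. They do not apply if both eyes are entered as separate observations.

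**The case against.** **The row is ambiguous.** It names no groups, it includes OSDI and SPEED, which are scheduled only at screening, and Table 3 describes its procedures as anticipated. If its t-test is paired, CLDEQ-8 loses essentially nothing. This is fair, but it shows that the plan does not settle the question. No other use of Mann-Whitney U is described, and no paired rank test is offered.

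**The steep fall in power comes partly from the set-up.** Holding the effect at 0.764 SD of the differences shrinks the raw lens difference from 0.764 × √2 = 1.08 SD at ρ = 0 to 0.764 × √0.4 = 0.48 SD at ρ = 0.8. With the raw difference fixed at 0.764 SD instead, Mann-Whitney U power is about 64 / 65 / 67 / 72 / 75% and signed-rank power about 62 / 77 / 88 / 98 / 99.8% (4,000 runs per cell). That is a proper qualification of the 20% and the 62 completers. The paired advantage remains: the two set-ups coincide at ρ = 0.5, and the gap stays wide above it.

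**The 90% benchmark is borrowed.** Section 4.2.1 takes its SD from scleral-vault and corneal-thickness work, so nothing shows that 20 was chosen for CLDEQ-8 or protease. This stands; 0.764 is a reference effect, not the plan's target.

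**Mann-Whitney U has a valid crossover use.** Applied to within-person period differences between the two lens-order groups, it also removes a period effect. With 10 per order and no period effect it has about 86 to 88% power. With a period effect of 0.764 SD of the differences and no lens effect, it rejects about 4 to 5% of the time. The signed-rank test then rejects about 1.5% at 10/10 and about 6 to 7% at 13/7. This is correct, and that analysis would be acceptable if stated, but Section 9.1 mentions neither sequence nor period.

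**Conclusion.** The concern holds. As written, the only rank test named for CLDEQ-8 and protease does not fit a design in which each participant wears both lenses, and the accompanying t-test is not stated to be paired. The error is conservative under positive correlation with one value per lens, so the risk is a missed difference, not a false positive.

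The size runs from nil at zero correlation to large: about 20 percentage points of power at 0.5 and more above that, for an approximately continuous outcome with 20 completers. The correlation is an assumption throughout. For a positive/negative protease reading the power argument is weak below high correlation. This should be corrected before any data are analysed, because it concerns primary outcomes and the correction is nearly free.

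**What to change.** In the second row of Table 3, for lens comparisons:

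- **CLDEQ-8, CLIQ and assayed protease:** name the Wilcoxon signed-rank test, or a t-test stated to be paired, on one coated-minus-uncoated value per participant. Choose one as the main test in advance.
- **Protease recorded as positive/negative:** name exact McNemar.
- **Alternative:** if Mann-Whitney U is kept, state that it compares within-person period differences between the two lens-order groups.

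In Section 9.1, add one or two sentences on the value analysed. One workable choice is the week-4 form for CLDEQ-8 and CLIQ and the mean of the two eyes for eye-level measures, with one pre-stated eye or rule for a positive/negative reading. Other choices would serve if fixed in advance.

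Two related edits belong in the same revision. Name CLIQ as a variable in this row, since it is a primary outcome and only quality of life appears, in the Analysis column. State that lens comparisons in the parametric row use the paired or repeated-measures test, not plain ANOVA.

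The cost is a rewording of Table 3 and those sentences. No extra data, participants or visits are needed.
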